7.8 Enrollment and Baseline

When a patient signs and dates the Consent Form, he/she is considered a subject enrolled in the study. The date the subject signed the Consent Form and data protection authorization must be documented. The following information is required to be collected at the Baseline visit:

- Medical history
- Pregnancy screen (if applicable)
- Physical exam
- 12 lead ECG (within 3 months of index ablation procedure)
- 48 hour ambulatory ECG monitor (within 3 months of index ablation procedure)
- Review of arrhythmic symptoms
- Review of antiarrhythmic drug use
- Neurologic evaluation
- MMSE
- Concomitant medication
- Cardioversion history
- Anticoagulation status; subjects are required to be prescribed to a vitamin K antagonist (VKA) 30 days prior to the ablation procedure.
 - Two therapeutic INR readings (≥ 2.0) within 30 days prior to the ablation procedure
- TTE (within 6 months of ablation procedure to determine LA size, LVEF, LV wall thickness)

- Randomize subject to [REDACTED] PVS assessment cohorts. Note that not all subjects may be selected for additional [REDACTED] PVS screening.

7.9 Phased RF Ablation Procedure

7.9.1 Pre-procedure evaluation

The following information is required to be collected at the ablation procedure or within specified timeframe prior to the ablation procedure:

- [REDACTED]
- Spiral CT or MRI of pulmonary veins for subjects randomized to PVS surveillance assessment cohort (Chest) (within 3 months prior to procedure). Spiral CT or MRI of pulmonary veins for subjects randomized to the PVS assessment cohort are only required for the index ablation procedure.
- Concomitant medications
- TEE to rule out left atrial thrombus (within 48 hours prior to procedure). If a left atrial thrombus is visualized during pre-procedure TEE, the study subject will not proceed to the study ablation procedure at that time.
- Visualize the esophagus prior to ablation
- INR (required to be 2.0 to 3.5 on the day of procedure)

NOTE: Other cardiac rhythm abnormalities requiring treatment in the right atrium may be detected during the Phased RF ablation procedure. When necessary for subject welfare, other approved ablation catheters may be utilized at the Investigator's discretion. Investigators are allowed to ablate arrhythmic triggers originating from the superior vena cava (SVC) and/or the cavotricuspid isthmus using indicated ablation catheter. Specifically, cavotricuspid isthmus ablation will be allowed providing one of the following criteria is satisfied:

- History of typical atrial flutter OR
- Inducible cavotricuspid isthmus dependent atrial flutter

The PVAC or PVAC GOLD catheter may be used to ablate within the SVC. All ablations will be documented on the ablation procedure CRF.

7.9.2 Procedure preparation

- Prior to transseptal puncture administer heparin bolus and start continuous heparin infusion to maintain ACT at or above 350 seconds
- Maintain continuous drip/flush of sheath when placed in left atrium
- Do not ablate with the Phased RF catheter unless ACT levels are at or above 350 seconds.

- Continue ACT measurements every 20-30 minutes thereafter until all Phased RF catheters are removed from body

7.9.3 *PVAC or PVAC GOLD catheter introduction*

- Pause continuous drip/flush of left atrial sheath
- Aspirate and flush the left atrial sheath prior to introduction of the catheter
- Follow catheter introduction and use instructions described in the instructions for use
- Capture the spiral array in the capture device while submerged in a saline and/or heparinized saline bath
- Aspirate and flush left atrial sheath once catheter array is beyond the sheath valve to exclude air ingress.
- Resume continuous drip/flush of left atrial sheath

7.9.4 *PVAC or PVAC GOLD pulmonary vein ablation*

- Follow instructions described in the catheter instructions for use and generator operator manual
- Map for pulmonary vein potentials
- Initiate ablation in 4:1, 2:1, or 1:1 mode only
- Verify isolation of the pulmonary veins after 30 minutes

7.9.5 *MASC catheter introduction*

- Pause continuous drip/flush of left atrial sheath
- Aspirate and flush the left atrial sheath prior to introduction of the catheter
- Follow catheter introduction and use instructions described in the instructions for use
- Capture the array in the capture device while submerged in a saline and/or heparinized saline bath
- Aspirate and flush left atrial sheath once catheter array is beyond the sheath valve to exclude air ingress.
- Resume continuous drip/flush of left atrial sheath

7.9.6 *MASC septal ablation*

- Follow catheter introduction and use instructions described in the instructions for use
- Map for arrhythmogenic tissue
- Initiate ablation in 1:1 ablation mode only
- Verify elimination of arrhythmogenic tissue

7.9.7 *MAAC catheter introduction*

- Pause continuous drip/flush of left atrial sheath
- Aspirate and flush the left atrial sheath prior to introduction of the catheter
- Follow catheter introduction and use instructions described in the instructions for use
- Capture the array in the capture device while submerged in a saline and/or heparinized saline bath

- Aspirate and flush left atrial sheath once catheter array is beyond the sheath valve to exclude air ingress.
- Resume continuous drip/flush of left atrial sheath

7.9.8 MAAC CFAE ablation

- Follow catheter introduction and use instructions described in the instructions for use
- Map for arrhythmogenic tissue
- Initiate ablation in 1:1 ablation mode only
- Verify elimination of arrhythmogenic tissue

7.9.9 Post-procedure evaluation

- 12 lead ECG
- Resume vitamin K antagonist (VKA) anticoagulation per subjects existing dose schedule
- Check INR at minimum every 12 hours until INR is ≥ 2.0

7.10 Discharge follow-up

- Physical Exam
- Neurologic evaluation
 - It is strongly recommended that the neurological evaluation be conducted after the effects of anesthesia subside
 - If evaluation identifies focal or global neurological deficit and/or signs/symptoms suggestive of stroke; then the following assessments are required:
 - NIHSS
 - MMSE
 - mRS
- 12 lead ECG
- Review of arrhythmic symptoms
- INR*
- Concomitant medications

***NOTE: subject cannot be discharged until INR is greater than or equal to 2.0 as per the HRS Consensus statement (After removal of all sheaths, warfarin should be reinitiated within four to six hours, and low-molecular weight heparin (LMWH) (enoxaparin 0.5–1.0 mg/kg twice daily) or intravenous heparin should be used as a bridge to resumption of INR 2.0–3.0).**

7.11 30 day follow-up

NOTE: 30 day follow up visit should occur as close to day 30 following the ablation procedure without occurring prior to day 30.

- Physical Exam
- Neurologic evaluation
 - If evaluation identifies focal or global neurological deficit and/or signs/symptoms suggestive of stroke; then the following assessments are required:
 - NIHSS
 - MMSE
 - mRS
- 12 lead ECG
- Review of arrhythmic symptoms
- INR
- Concomitant medications
- [REDACTED]
- [REDACTED]
- Cardioversion history

7.12 3 month follow-up

- Physical Exam
- Neurologic evaluation and assessments for subjects previously diagnosed with a focal or global neurological deficit and/or signs/symptoms suggestive of stroke; assessments include:
 - NIHSS
 - MMSE
 - mRS
- 12 lead ECG
- Review of arrhythmic symptoms
- INR
- Concomitant medications (amiodarone required to be stopped at this visit)
- Cardioversion history
- MRI or CT scan (Chest) for subjects in the PVS assessment cohort; subjects randomized to the PVS assessment cohort will receive a 3-month CT or MRI scan at their first 3-month post-ablation visit (e.g. if a subject is reablated after the initial 3-month post-ablation visit, a second CT scan for PVS screening is not required at the 3-month post-reablation visit). The same scanning technology should be used for the baseline and 3 month PVS assessment.
- [REDACTED]

7.13 6 month follow-up

- Physical Exam
- Neurologic evaluation and assessments for subjects previously diagnosed with a focal or global neurological deficit and/or signs/symptoms suggestive of stroke; assessments include:
 - NIHSS
 - MMSE
 - mRS
- 12 lead ECG
- 48 hour ambulatory ECG monitor. Note: the same ambulatory ECG monitoring technology used at the Baseline visit should be used at the 6-month follow-up visit. Subjects may be asked to repeat an ambulatory ECG monitoring session if less than 24 hours of analyzable monitoring time is obtained.
- Review of arrhythmic symptoms
- INR
- Concomitant medications
- Cardioversion history

7.14 Unscheduled follow-up visits

An unscheduled visit is defined as any unplanned office visit at the study site that occurs between protocol required visits. The requirements at an unscheduled visit are:

- Physical Exam
- Neurologic evaluation
 - If evaluation identifies focal or global neurological deficit and/or signs/symptoms suggestive of stroke; then the following assessments are required:
 - NIHSS
 - MMSE
 - mRS
- 12 lead ECG
- Review of arrhythmic symptoms
- INR
- Concomitant medications
- Cardioversion history

7.15 Permissible Retreatment Ablation Procedure

All study subjects may have one reablation procedure with the Phased RF System within 180 days of their index ablation procedure under this protocol if the following criteria are met:

- Subject has not completed the 6-month follow-up visit
- Recurrent AF/AFL that cannot be controlled with antiarrhythmic drugs and/or cardioversion
- The subject has not had any other ablation procedure in the left atrium since first Phased RF ablation
- Subjects undergoing a retreatment procedure are willing to be followed for 6-months following their retreatment procedure, or until official study closure defined as when Medtronic and/or regulatory requirements have been satisfied per the Clinical Investigational Plan, whichever occurs first. Medtronic will provide a new set of target visit dates following notification of a retreatment procedure as described in section 7.6.

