6.2.3 Secondary safety objective

6.2.3.1 Pulmonary vein stenosis (PVS)

Characterize the incidence of PVS 3 months post ablation procedure as determined by MRI or CT scan.

This objective will be evaluated in a subset of 100 subjects.

6.3.1 *Inclusion criteria*

1. History of symptomatic persistent or long-standing persistent atrial fibrillation defined as:
 - Persistent AF: sustained AF lasting > 7 days but no more than 1 year, or sustained AF lasting < 7 days but necessitating pharmacologic or electrical cardioversion; OR
 - Long-standing persistent AF: sustained AF lasting at least 1 year but no more than 4 years in duration.AND
 - Continuous AF as demonstrated on a 48-hour ambulatory ECG monitor at baseline AND
 - AF symptoms defined as the manifestation of:
 - Palpitations
 - Fatigue
 - Exertional dyspnea
 - Increased intolerance to routine activities (exercise intolerance)
2. Age 18-75 years
3. Failure of at least one class I or III anti-arrhythmic drug (AAD)
4. Willingness, ability and commitment to participate in baseline and follow-up evaluations for the full length of the study

6.3.2 *Exclusion criteria*

1. Structural heart disease of clinical significance including:
 - Previous cardiac surgery (e.g. mitral valve repair) except CABG
 - NYHA Class III or IV CHF and/or documented ejection fraction <40% measured by acceptable cardiac testing (e.g. TEE)
 - Left atrial diameter of >55mm
 - 3+ mitral or aortic valvular heart disease
 - Stable/unstable angina or ongoing myocardial ischemia
 - Myocardial infarction (MI) within three months of enrollment
 - Congenital heart disease other than ASD or PFO without a right to left shunt where the underlying abnormality increases the risk of an ablative procedure
 - Prior ASD or PFO closure with a device using a percutaneous approach
 - Hypertrophic cardiomyopathy (LV septal wall thickness >1.5 cm)

- Pulmonary hypertension (mean or systolic PA pressure >50mm Hg on Doppler echo)
2. Any prior ablation for atrial fibrillation in the left atrium
 3. Enrollment in any other ongoing arrhythmia study protocol
 4. Any ventricular tachyarrhythmia currently being treated where the arrhythmia or the management may interfere with this study
 5. Active infection or sepsis
 6. History of symptomatic cerebral vascular disease such as clinical stroke, TIA or other diseases that manifest stroke-like symptoms (e.g. multiple sclerosis or seizure disorders)
 7. Pregnancy or lactation

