6.4 Minimization of Bias

Selection of subjects, treatment of subjects, and evaluation of study data are potential sources of bias. Methods incorporated in the study design to minimize potential bias include (but are not limited to):

- Subjects will be screened to confirm eligibility for enrollment with defined inclusion/exclusion criteria prior to enrollment.
- Subjects will be selected randomly (excluding the first enrolled subject at each center) for evaluating the incidence of [REDACTED] pulmonary vein stenosis.
- Demographics and medical history will be collected at baseline in order to later assess possible characteristics that may influence study endpoints.

- Data collection requirements and study procedures will be standardized across all study centers.
- No more than 15% (45) of ablated study subjects may come from a single center.
- No more than 33% (100) of ablated study subjects may come from geographies outside the US.
- All study center and Medtronic personnel will be trained using standardized training materials.
- All study clinicians will be trained on and required to follow the Clinical Investigation Plan.
- All study investigators will be required to meet the requirements of 21 CFR Part 54, Financial Disclosure by Clinical Investigators.
- Regular monitoring visits will be conducted to verify source data and adherence to the Clinical Investigation Plan and source data.
- A core laboratory will be used to characterize [REDACTED] all baseline and 6-month follow-up 48-hour ambulatory ECG monitors
- [REDACTED]
- A core laboratory will be used to evaluate CT or MRI images for pulmonary vein stenosis at baseline and at the 3-month post-procedure follow-up visit.
- An independent clinical events committee (CEC) will be utilized to regularly review and adjudicate reported adverse events.
- An independent data monitoring committee (DMC) will be utilized to review accumulating safety data, help safeguard the interests of study subjects, and monitor the overall conduct of the study

In summary, potential sources of bias that may be encountered in this clinical investigation have been considered and minimized by careful study design.

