7.5 Data collection

Clinical data is collected at designated time points throughout the study. Data will be collected using an electronic data management system for clinical studies. Data will be stored in a secure, password-protected database which will be backed up nightly. Data will be reviewed using programmed and manual data checks. Data queries will be made available to study centers for resolution. Study management reports may be generated by Medtronic to monitor data quality and study progress. At the end of the study, the data will be frozen and retained indefinitely by Medtronic. Data collection requirements are summarized in Table 6 below.

Table 6: Data collection and study procedure requirements at subject visits

	Ablation Procedure				Repeat Ablation Procedure (1-180 days)				30 day	3 month	6 month	Unscheduled
	Baseline	Procedure	Post-procedure	Discharge	Baseline	Procedure	Post-procedure	Discharge				
Consent	X											
Incl/Excl Criteria	X											
History	X											
Physical exam	X(11)			X	X			X	X	X	X	X
Pregnancy Screen (if applicable per local requirement)	X											
Standard neurologic evaluation (performed by neurologist)	X			X	X			X	X	X(10)	X(10)	X
Concomitant medications	X		X	X	X			X	X	X	X	X
Arrhythmic Sx review	X				X				X	X	X	X
12 lead ECG	X(11)			X	X			X	X	X	X	X
Cardioversion log	X				X				X	X	X	X
TTE	X(2)				X(2)							
Esophageal visualization		X				X						
MRI or CT for PVS	X(3, 11)									X(3)		
██████████		████		████					████			
NIHSS (performed by neurologist)				X(1)				X(1)	X(1)	X(1)	X(1)	X(1)
MMSE (performed by neurologist)	X			X(1)				X(1)	X(1)	X(1)	X(1)	X(1)
mRS (performed by neurologist)				X(1)				X(1)	X(1)	X(1)	X(1)	X(1)
INR	X	X	X	X	X	X	X	X	X	X	X	X
ACT		X				X						
48 hour ambulatory ECG monitoring	X(11)										X	
TEE		X(5)				X(5)						
AE review		X	X	X	X	X	X	X	X	X	X	X
GENius Data File Collection		X				X						

1. Only for subjects diagnosed with protocol defined stroke
2. Not required for repeat ablation procedures as long as last TTE was performed within 6 months of reablation procedure
3. Only required for the subset subjects in the PVS assessment cohort. The same technology should be used for baseline and 3 month scans

5. Required 48 hours prior to ablation procedure

10. Only for subjects that have been diagnosed with a focal or global neurological deficit and/or signs/symptoms suggestive of stroke
11. Must be completed within 3 months prior to index ablation procedure

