12.2.6 Sample size and power

[figure not shown]
A sample size of 300 subjects completing the 30-day post procedure follow-up visit and having the opportunity for a reablation procedure (i.e. completing the 6-month follow-up visit) or having a reablation procedure and completing the 30-day post-reablation visit provides at least 80% power to test the primary study hypothesis given the following assumptions:

1. One-sided type I error rate of 0.05
2. Exact test of a binomial proportion versus a fixed performance goal of 3.5%
3. Observed stroke rate must be less than 1.8%.
4. Assumed true stroke rate is 1.3%

Figure 1 displays the power of the study to meet its primary objective when the true stroke rate ranges from 0.1% to 3.5% and 300 subjects complete the 30-day post-ablation (or reablation) visit and have had the opportunity for a reablation procedure. Specifically, the study has 90% power if the true stroke rate is 1%, 80% power if the true stroke rate is 1.3%, and 55% power if the true stroke rate is 1.8%. Figure 1 also demonstrates that the type I error is less than 5% when the true stroke rate is 3.5%.

Assuming an annualized attrition rate of 10% following the index ablation procedure, a uniform reablation rate of 30% within 180 days of the index ablation procedure, and a conservative 26% pre-procedure attrition rate up to 420 enrolled subjects will be required to ensure that at least 300 subjects complete the 30-day post ablation follow-up visit and have the opportunity for a reablation procedure or have a reablation procedure and complete the 30-day post-reablation procedure visit. Note that it is not anticipated that all 420 subject enrollments will be required, since study enrollment will cease once enough subjects have completed an index Phased RF procedure to ensure that the target sample size of 300 evaluable subjects can be obtained.

Figure 1: Study Power versus True Stroke Rate

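### Reablation is allowed up to day 180 with no bar for a stroke or TIA since the index procedure, and no pregnancy screen is scheduled before it

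*Protocol*

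**What the plan says.** Protocol 7.15: "All study subjects may have one reablation procedure with the Phased RF System within 180 days of their index ablation procedure", subject to four criteria. The 6-month visit has not been completed; AF/AFL has recurred and is not controlled by drugs or cardioversion; there has been no other left atrial ablation since the first; and the subject accepts a further 6 months of follow-up, or follow-up to study closure. The section does not mention stroke, TIA or pregnancy and does not refer back to the exclusion criteria.

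Protocol 6.3.2 excludes at entry "History of symptomatic cerebral vascular disease such as clinical stroke, TIA or other diseases that manifest stroke-like symptoms" (no. 6) and pregnancy or lactation (no. 7). Section 6.4 fixes the time of that check: "Subjects will be screened to confirm eligibility for enrollment with defined inclusion/exclusion criteria prior to enrollment".

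Table 6 (Protocol 7.5) gives the repeat procedure its own block with its own Baseline column. The row "Incl/Excl Criteria" and the pregnancy screen row each carry a single mark, under the index Baseline. Section 7.8 lists the pregnancy screen for Enrollment and Baseline, and the pre-procedure list in 7.9.1 omits it. Section 7.7 requires a test in women of child-bearing potential but names no visit.

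The repeat Baseline is not empty. It has a physical exam, an evaluation by the neurologist, medication and symptom review, 12-lead ECG, cardioversion log, INR and adverse event review, plus a TTE if the last one is more than 6 months old. TEE, INR and ACT follow at the repeat procedure.

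**The concern.** The study was set up because an advisory panel was concerned about peri-procedural stroke with this system (Protocol 3). A patient with a TIA before enrollment is kept out. A subject with a TIA after the index procedure still meets 7.15 and may have the same left atrial procedure again. TIA is not a primary endpoint event (Protocol 6.2.1), so the first event goes uncounted, while a related stroke within 30 days of the reablation counts and would be hard to interpret.

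On pregnancy, the age range starts at 18, sites are urged to enroll women (7.2), and fluoroscopy is used for catheter placement (Table 14). A site that follows the schedule exactly could perform a second procedure on a woman whose last test preceded the index ablation.

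**Working it through.** **1. Can the enrollment exclusions be read as carrying over to reablation?** No. Exclusion 2 bars any prior left atrial ablation for AF, so carrying the list over would forbid every reablation that 7.15 allows. The infarction exclusion is worded "Myocardial infarction (MI) within three months of enrollment", so its window does not move to the reablation date. Section 7.15 has to stand alone.

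**2. Which scheduled checks stop a reablation?** Left atrial thrombus on TEE (7.7, 7.9.1), an INR outside 2.0 to 3.5 on the day (7.9.1), and an ACT below 350 seconds before energy is delivered (7.9.2). The exam, neurologic evaluation, ECG and adverse event review can find a problem, but no rule says what follows. Withdrawal under 7.16 is optional. Section 9 defines a deviation as something not done according to the plan, so reablating a subject after a TIA, with 7.15 met, would not be one.

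**3. Timing and scale.** Inputs: "a uniform reablation rate of 30% within 180 days of the index ablation procedure" (Protocol 12.2.6) and 300 evaluable subjects. Attrition is ignored.

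- Reablations: 0.30 × 300 = 90.
- Mean time from index: 180 / 2 = 90 days.
- Share after day 90: (180 − 90) / 180 = 50%, so 0.5 × 90 = 45.
- Age of the last scheduled pregnancy screen: at least the days since index, so at least 180 days at day 180.

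The documents give no rate for post-index stroke or TIA among candidates for reablation, nor for pregnancy, so the number affected cannot be derived.

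**4. The primary test.** Success requires an observed rate below 1.8% and an exact one-sided 95% upper bound below 3.5%. With n = 300:

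- 5 strokes: 5/300 = 1.67%, bound 3.47%, pass.
- 6 strokes: 6/300 = 2.00%, bound 3.91%, fail.

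Power is therefore P(X ≤ 5), with X binomial (300, π):

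| True rate | Stated | Recomputed |
|---|---|---|
| 1% | 90% | 91.7% |
| 1.3% | 80% | 80.2% |
| 1.8% | 55% | 54.6% |
| 3.5% (type I error) | below 5% | 4.76% |

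The plan's figures are reproduced, and no reablation criterion enters them.

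**5. Direction.** The numerator counts subjects (12.2.5). A subject already counted for an index stroke adds nothing through a second one. Only a subject whose first event was not counted, such as a TIA, can add to the numerator. The present rule can therefore only raise the observed rate. A bar works the other way: each stroke avoided is 1/300 = 0.33 percentage points, and the pass line lies between 5 and 6.

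**The case against.** The case against is substantial, and it limits the point.

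- *Section 7.15 permits; it does not direct.* No investigator is obliged to reablate, and 7.16 offers withdrawal when medically justified. This stands, but it leaves the decision unwritten for a condition that the protocol treats as disqualifying at entry.
- *Detection is already scheduled.* For infarction and infection this largely answers the concern: the exam, ECG and adverse event review should reveal them, and a written bar would mostly record ordinary clinical judgement. For stroke or TIA the neurologist's evaluation helps, but nothing ties a finding to the decision. No scheduled item tests for pregnancy.
- *Section 7.7 already requires a pregnancy test.* It gives partial cover, because it names no visit. Section 7.8 and Table 6 place the test at index Baseline, and Table 6 makes it depend on local requirement.
- *Unseen documents.* The instructions for use and the consent form may add protection. They were not available for this review.
- *The remedy has side effects.* In Europe the system is market released, so a barred subject could be reablated commercially, outside study follow-up. If a non-investigational catheter then entered the left atrium, 12.2.7 could remove the subject from the primary analysis. This stands and belongs in the fix.

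A reader might infer more than the documents support. They do not show that reablations go ahead unassessed; the repeat Baseline is well populated. They do not show a risk of false success; step 5 gives the opposite direction. The 90 and 45 are all reablations, not subjects at risk. Nor does the gap call for re-applying every entry criterion: that would bar all reablations through exclusion 2 and would require continuous AF on a 48-hour monitor that is not scheduled at that point.

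**Conclusion.** The concern holds for two items. Section 7.15 does not bar reablation after a stroke or TIA since index, and no pregnancy screen is scheduled before a reablation that may come up to 180 days after the index procedure. It does not extend with the same force to infarction or infection. Lactation can hardly arise anew within 180 days of a negative baseline.

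The number of affected subjects is not estimable. The timing figures rest on the protocol's own assumption of 30% reablation spread evenly over 180 days. Sample size, power and test are unchanged. This is a minor, inexpensive improvement for subject safety and for the interpretation of strokes after reablation, subject to what the instructions for use and consent form may already say.

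**What to change.** 1. In Table 6, mark the Pregnancy Screen in the Repeat Ablation Baseline column for women of child-bearing potential, and state that a positive test bars reablation.
2. In 7.15, add that a subject with a stroke or TIA since the index procedure is not eligible for in-study reablation.
3. Optionally add infarction within 3 months before the reablation and active infection to the same list. Leave lactation out, and do not re-mark the full inclusion/exclusion row.
4. Report the number of subjects barred, so that a reader can judge whether the bar affected the observed stroke rate.

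The cost is one table mark, one sentence, and a pregnancy test where applicable. The stroke/TIA item uses assessments already scheduled. A few subjects would lose in-study reablation, and some in Europe might be treated commercially beyond the study's anticoagulation rules and neurologic follow-up. Removing possibly higher-risk reablations could also lower the observed stroke rate slightly, in the sponsor's favour, which is the reason for item 4.
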